9.3 General considerations

All data obtained in this trial and documented in the eCRFs will be listed and summarized with statistics or frequency tables as appropriate. In case of termination of the trial, all data collected up to that timepoint will be included in the analysis.

Raw data listings and summary tables will be generated using the software SAS[©] version 9.4 or higher.

Continuous variables will be summarized using means, standard deviations, medians, coefficients of variation, and minimum and maximum values.

Other summaries (e.g. quartiles, 95% confidence intervals [CIs]) may be used as appropriate. Categorical efficacy and safety variables will be summarized by counts and by percentage of subjects in corresponding categories.

9.4 Demographics and baseline characteristics

Baseline and demographic data will be summarized using descriptive statistics. Baseline ADA-positive subjects will be calculated as a percentage of the total number of subjects whose baseline samples were tested for ADA.

All other data obtained in this trial and documented in the eCRF will be listed.

9.5 Efficacy Analyses

For the confirmatory analyses, the primary and key secondary endpoints for the dasiglucagon 0.6 mg and placebo treated subjects will be compared. A hierarchical procedure will be applied for the control of multiplicity. The primary and secondary endpoints will be evaluated on the full analysis set. In the primary analysis, those subjects who require rescue IV glucose will be censored at the time to plasma glucose recovery. In a sensitivity analysis, the time to plasma glucose recovery will be analyzed without censoring the subjects who received rescue IV glucose.

9.5.1 Hierarchical testing procedure

For the confirmatory analyses, the following a priori defined hierarchical inferential test order will be applied for the control of the type 1 error rate across the planned multiple comparisons. The primary endpoint and key secondary endpoints will be inferentially evaluated within the FAS in the following order, where inference will proceed at the two-sided 0.05 criterion significance level until the first failure to reject the null hypothesis for a dasiglucagon versus placebo comparison:

- Primary: Time to plasma glucose recovery
- Key secondaries 1-4: Plasma glucose recovery within 30 minutes, within 20 minutes, within 15 minutes, and within 10 minutes after study drug injection without administration of rescue IV glucose.
- Key secondaries 5-8: Plasma glucose changes from baseline (CFB) within 30 minutes, within 20 minutes, within 15 minutes, and within 10 minutes after study drug injection or at the time of rescue.

The GlucaGen versus placebo comparisons will not be included in the inferential testing hierarchy, since the efficacy of GlucaGen is previously established, and these comparisons are intended to support the validity of the study for the dasiglucagon versus placebo comparisons.

Analogous supportive sensitivity analyses will be conducted in the PP set, but without inference intent.

9.5.2 Primary confirmatory endpoint

Time to plasma glucose recovery. Plasma glucose recovery is defined as first increase in plasma glucose of ≥ 20 mg/dL (1.1 mmol/L) from baseline during the hypoglycemic clamp procedure without administration of rescue IV glucose.

9.5.2.1 Primary analysis

The primary endpoint will be summarized using Kaplan-Meier (KM) estimates stratified by treatment group and injection site. The treatment group difference between dasiglucagon and placebo will be evaluated inferentially using a pairwise two-sided log-rank test.

In the primary analysis, those subjects who require rescue IV glucose will be censored at the time of plasma glucose recovery. This approach is based on the assumption that rescue IV glucose administration will shorten the time to recovery. This assumption implies that censoring at the time of recovery after rescue therapy is valid as a time to

recovery without rescue would be longer than the observed duration. If recovery has not occurred at 45 minutes after study drug injection, censoring will be applied irrespective of the use of rescue IV glucose.

In sensitivity analyses, the time to plasma glucose recovery will be analyzed 1) without censoring at the time of recovery for those subjects who require rescue IV glucose before 45 minutes and 2) with censoring at the time of administration of rescue IV glucose before 45 minutes.

The primary endpoint will additionally be analyzed using a Cox proportional hazards (CPH) time to event statistical model, if the hazards by treatment group can be assumed proportional using a graphical comparison of log-minus-log survival curves and no more than two-thirds of the recovery times are censored in each treatment group. The CPH model will be used for inferences, with treatment group and injection site modeled as categorical effects, and baseline plasma glucose modeled as a continuous covariate. The treatment group rate ratios, active versus placebo, will be estimated together with the 95% confidence intervals, and pairwise treatment group inferences (dasiglucagon vs placebo, GlucaGen vs placebo) will be evaluated using two-sided likelihood ratio tests.

9.5.3 Secondary endpoints

- Plasma glucose recovery within 30 minutes, within 20 minutes, within 15 minutes, and within 10 minutes after study drug injection without administration of rescue IV glucose.
- Plasma glucose changes from baseline within 30 minutes, within 20 minutes, within 15 minutes, and within 10 minutes after study drug injection or at the time of rescue.

9.5.3.1 Confirmatory analysis

The key secondary incidence variables (plasma glucose recovery within 30 minutes, within 20 minutes, within 15 minutes, within 10 minutes, in hierarchical order for inference) will be analyzed using descriptive statistics (frequency and percentage) by treatment group. Inferential treatment group comparisons will be assessed via pairwise tests of independent binomial proportions (dasiglucagon versus placebo, GlucaGen versus placebo) using Fisher's exact test for each pairwise comparison.

The key secondary endpoints of plasma glucose CFB within 30 minutes, within 20 minutes, within 15 minutes, and within 10 minutes after study drug injection or at the time of rescue, will be analyzed with the plasma glucose CFB at rescue carried forward in those subjects who require rescue IV glucose before plasma glucose ≥ 20 mg/dL recovery. Each of these CFB variables will be analyzed using an Analysis of Covariance model, with treatment group modeled as a fixed effect and with the baseline plasma glucose modeled as a covariate. The dasiglucagon versus placebo treatment group difference will

be evaluated inferentially as a least squares means contrast, using a two-sided t-test at the 0.05 significance level, first for the 30 minute CFB, and then sequentially for the 20 minute, 15 minute, and 10 minute variables, until the first failure to reject.

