Plasma glucose concentrations will be measured using a US FDA-approved glucose analyzer (e.g., YSI 2300, Yellow Springs Instruments, Yellow Springs, OH). After the start of the insulin infusion, plasma glucose will be measured every 10 minutes while plasma glucose is above 110 mg/dL, and every 5 minutes once plasma glucose is at or below 110 mg/dL.

Once the glucose concentration declines to <60 mg/dL (3.3 mmol/L), the insulin infusion will be stopped, and 5 min later plasma glucose concentration will be measured at the glucose analyzer and blood samples for baseline assessment of plasma glucose, dasiglucagon/GlucaGen PK, and insulin PK will be collected. The samples are the baseline samples and should be collected within 2 minutes before IMP administration.

- If plasma glucose is ≥ 45 mg/dL and < 60 mg/dL (2.5-3.3 mmol/L), study treatment (IMP) will be administered, defining time, $t=0$. The study treatment will be delivered in the abdomen, buttock, or thigh (according to stratification) via SC injection, with the subject lying in a lateral recumbent position.
- If plasma glucose is < 45 mg/dL (2.5 mmol/L), IV glucose solution will be administered sufficient to raise plasma glucose to within the 45-60 mg/dL target range. The run-in period will be adequately extended (at least 30 min) until the above target is achieved and new baseline samples for plasma glucose, dasiglucagon/GlucaGen PK, and insulin PK will be collected. Glucose should not be infused within 10 minutes before IMP administration. If plasma glucose is not within target range after the second attempt, the subject should be rescheduled for a new treatment visit within 7 days (+ 2 days).

Administration of IMP should not occur earlier than 9:00 hours in the morning or later than 12:00 hours.

As shown in **Table 4**, serial blood samples for glucose will be collected at $t=0, 4, 6, 8, 10, 12, 15, 17, 20, 25, 30, 40, 50, 60, 75$ and 90 minutes post-dosing. Samples for assessing plasma dasiglucagon/GlucaGen concentration will be collected at $t=0, 15, 30, 35, 40, 50,$

60, 90, and 120 minutes. Samples for assessing plasma insulin concentration will be collected at t=0, 30, and 60 minutes.

Table 4 Post-treatment blood sampling times

Times	0	4	6	8	10	12	15	17	20	25	30	35	40	50	60	75	90	120
Plasma glucose	Y	Y	Y	Y	Y	Y	Y	Y	Y	Y	Y		Y	Y	Y	Y	Y	
PK Dasiglucagon/ Glucagon	Y						Y				Y	Y	Y	Y	Y		Y	Y
PK Insulin	Y									Y				Y				

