9.7.4 Other safety data

Incidence of rescue infusion of IV glucose during the hypoglycemic clamp procedure will be analyzed using descriptive statistics (frequency and percentage) by treatment group. Inferential treatment group comparisons will be assessed via pairwise tests of

independent binomial proportions (dasiglucagon versus placebo, GlucaGen versus placebo).

Time to first rescue infusion of IV glucose during the hypoglycemic clamp procedure will be evaluated using a KM time to event statistical model, with treatment group and injection site as stratification factors. Differences between the KM curves (dasiglucagon versus placebo, GlucaGen versus placebo) will be evaluated inferentially using pairwise two-sided stratified log-rank tests. If the endpoint is never met, the time of the last plasma glucose measurement will be the censoring time.

Vital signs, physical examination, 12-lead ECG and local tolerability data will be summarized using descriptive statistics.

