6.2 Treatment assignment and randomization

Subjects successfully completing screening and who fulfill entry eligibility and randomization criteria will be randomized to one of three treatment groups in a ratio of 2:1:1:

- Test treatment: Dasiglucagon, liquid formulation, 1 mg/mL, 0.6 mL delivered in a prefilled syringe.
- Placebo treatment: Placebo, liquid formulation, 0.6 mL delivered in a prefilled syringe.
- Reference treatment: Recombinant glucagon hydrochloride, 1 mg for reconstitution.

Randomization will be performed using a fixed-block randomization scheme. The randomization scheme will be generated prior to the initiation of the study by an independent statistician/programmer who will not be a member of the study team; all investigators will not be aware of the block size of the randomization scheme.

Randomization will be stratified by treatment group and by injection site (abdomen, buttocks, or thigh) and controlled via the IWRS.

Subjects will be randomized to study treatment using an interactive, automated system which has been validated for the intended use under the International Society of Pharmaceutical Engineers Good Automated Manufacturing Process guidelines, 21CFR Part 11 (FDA regulation for Electronic Records and Electronic Signatures) and the International Conference on Harmonization (ICH) Guidance E6 for Industry on Good Clinical Practice (GCP).

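### Randomisation is stratified by injection site, but the confirmatory tests leave site out or do not say that they use it; adding it is a free improvement

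*Protocol*

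**What the plan says.** Design. Section 6.2 states: "Randomization will be stratified by treatment group and by injection site (abdomen, buttocks, or thigh) and controlled via the IWRS". Treatment group cannot be a stratification factor for its own allocation, so injection site, with three levels, is the only real stratum. Section 6.2 is shown only in the earlier protocol versions in the file. The most recent text carries the stratum forward in 8.2.3.1: "The study treatment will be delivered in the abdomen, buttock, or thigh (according to stratification) via SC injection".

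Where site is used:
- The primary endpoint is "summarized using Kaplan-Meier (KM) estimates stratified by treatment group and injection site" (9.5.2.1).
- The additional Cox model, which is conditional on proportional hazards and on limited censoring, is fitted "with treatment group and injection site modeled as categorical effects" (9.5.2.1).
- Time to first rescue infusion, a safety endpoint, has injection site as a stratification factor, and the curve differences "will be evaluated inferentially using pairwise two-sided stratified log-rank tests" (9.7.4).

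Where site is absent or not stated:
- Primary test (9.5.2.1): "The treatment group difference between dasiglucagon and placebo will be evaluated inferentially using a pairwise two-sided log-rank test". No stratification is named.
- Key secondaries 1-4, the recovery proportions (9.5.3.1): "Fisher's exact test for each pairwise comparison".
- Key secondaries 5-8, change from baseline (9.5.3.1): ANCOVA "with treatment group modeled as a fixed effect and with the baseline plasma glucose modeled as a covariate".
- AUC from 0 to 30 minutes (9.5.4.1): ANCOVA on the log scale with treatment and baseline glucose only.

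**The concern.** None of the nine steps in the testing hierarchy (9.5.1) is stated to use the factor by which subjects are randomised. When allocation is balanced within strata and the stratum predicts outcome, an analysis that ignores it leaves between-stratum variation in the error term. The usual results are standard errors that are too large, tests that run below their nominal level, and some lost power.

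The plan is also uneven: a safety endpoint gets an explicitly stratified log-rank test, while the primary endpoint gets one whose stratification is left unsaid. Two analysts could read 9.5.2.1 differently and report different primary p-values. What is at stake is precision and clarity, not validity.

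**Working it through.** **1. The plan's own figure.** Inputs from 9.1: 78 versus 39 subjects, 80% versus 50% recovery within 20 minutes, two-sided 5%, stated power 90%.
- Pooled rate = (78×0.8 + 39×0.5)/117 = 0.70.
- SE under the null = √(0.7×0.3×(1/78 + 1/39)) = 0.0899.
- SE under the alternative = √(0.8×0.2/78 + 0.5×0.5/39) = 0.0920.
- Power = Φ((0.30 − 1.96×0.0899)/0.0920) = 91.1%.
- Exact enumeration of Fisher's test gives 88.9%.

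The stated 90% reproduces and is not in dispute.

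**2. Assumptions for the rest.** The documents give no injection-site effect, so a range is shown. Subjects are taken as split equally over sites (26 versus 13 at each). Under exponential times the planning rates imply a rate ratio of ln(0.2)/ln(0.5) = 2.32.

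**3. Log-rank test.** Simulation used the protocol's glucose sampling times, with censoring at 45 minutes and a rate ratio of 2.32. There were 1,500 to 2,000 runs per setting, so power carries a Monte Carlo error of up to about 1 point. A log-rate step of 0.5 between neighbouring sites means site rate ratios of about 1.65/1/0.61; a step of 1.0 means about 2.72/1/0.37.

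| Site effect on recovery rate | Unstratified | Stratified |
|---|---|---|
| None | 97.5% | 97.5% |
| Log step 0.25 | 97.1% | 97.2% |
| Ratios 1.3/1/0.77 | 97.1% | 97.3% |
| Ratios 1.6/1/0.63 | 95.6% | 97.1% |
| Log step 0.5 | 94.3% | 96.7% |
| Ratios 2/1/0.5 | 91.6% | 96.4% |
| Log step 1.0 | 80.6% | 94.8% |

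The loss is 0.1 to 2.4 points up to a log step of 0.5. It reaches 4.8 points when rates differ fourfold between the extreme sites, and 14.2 points when they differ about sevenfold (e² = 7.4). Under no treatment effect the unstratified test rejected in 4.0%, 5.0%, 4.5% and 1.7% of runs at log steps of 0, 0.25, 0.5 and 1.0, so there is no sign of inflation and the test is conservative at the largest step.

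**4. Recovery within 20 minutes.** The marginal rates of 80% and 50% were held, with site shifts of −s, 0 and +s on the logit scale and 20,000 runs. The unstratified Mantel-Haenszel (MH) column separates Fisher's own conservatism from the effect of the stratum.

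| s | Power: Fisher | Power: unstratified MH | Power: site-stratified CMH | Type I error at 50%/50%: Fisher | Type I error at 50%/50%: CMH |
|---|---|---|---|---|---|
| 0 | 89.0% | 91.0% | 91.3% | 4.3% | 4.8% |
| 0.5 | 89.4% | 91.2% | 92.1% | 3.8% | 5.0% |
| 1.0 | 90.3% | 92.2% | 94.1% | 2.9% | 4.7% |
| 1.5 | 91.8% | 93.8% | 96.6% | 1.9% | 5.0% |

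About 2 points of each gap between Fisher and CMH come from Fisher's discreteness. The part due to the stratum is 0.3, 0.9, 1.9 and 2.8 points.

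**5. ANCOVA.** If site explains a share R² of residual variance, the SE without site is too large by 1/√(1 − R²) − 1.
- R² = 5%: 1/√0.95 − 1 = 2.6%
- R² = 10%: 1/√0.90 − 1 = 5.4%
- R² = 15%: 1/√0.85 − 1 = 8.5%

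From a 90% base, power with site in the model is Φ((1.96 + 1.2816)/√(1 − R²) − 1.96): 91.4% at R² = 5% and 92.7% at 10%.

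**The case against.** **No site effect is documented.** This stands. If site does not matter, nothing is lost. Differential absorption from the injection site could not act in the placebo arm, which contains no active substance. With an effect confined to the active arm, of a size that would explain about 5 to 15% of residual variance if it acted in both arms, the ANCOVA power gain is only about 0.6 to 1.5 points from a 90% base. For the log-rank test, the same restriction does not shrink the gap.

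**The log-rank test may already be meant as stratified.** The sentence just before it stratifies the Kaplan-Meier estimates by site, and Section 9 lets the SAP refine details. This stands in part. A reader might infer that the primary test is definitely unstratified; the text does not settle that, and the contrast with 9.7.4 only makes it the more literal reading. The Fisher tests and the ANCOVAs are different: the protocol names the test or lists the covariates, so site is left out rather than left open.

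**Larger losses can be produced.** A reader who takes a treatment rate ratio of 1.75 can obtain log-rank power of 57% unstratified against 71% stratified at site ratios of 2/1/0.5. That rate ratio appears nowhere in the protocol and is weaker than the planning rates imply.

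**Fisher's low actual size.** It is about 3.9 to 4.3% at common rates of 50 to 70%. A reader might blame the missing stratum, but those values arise from discreteness with no site effect at all. An exact test is also defensible when cells are sparse: in phase 2 every subject recovered within 30 minutes (2.1.3.1), and here there would be about 13 placebo subjects per site. That bears on the form of the replacement test, not on whether to stratify.

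**Conclusion.** The point holds as a free improvement. The key secondary Fisher tests, the change-from-baseline ANCOVAs and the AUC ANCOVA omit the randomisation stratum, and the primary log-rank test does not say whether it uses it. If site is prognostic, these analyses are conservative. At the planning effect and with equal site sizes, the log-rank loss is nil with no site effect, about 0 to 2 points for weak to moderate effects, and about 5 to 14 points only when sites differ strongly. The ANCOVA standard errors are a few percent too large over the range shown.

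A reader might infer that the hierarchy is invalid or the trial underpowered. Neither follows: any departure from the nominal level is towards conservatism, and the stated 90% power reproduces. The size of any gain rests on an assumed site effect, for which the documents give no figure.

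**What to change.** - **9.5.2.1:** state that the primary log-rank test is stratified by injection site, as 9.7.4 already does for time to rescue.
- **9.5.3.1, recovery proportions:** replace Fisher's test by a Cochran-Mantel-Haenszel test stratified by injection site, in its exact form where cells are sparse.
- **9.5.3.1 and 9.5.4.1, ANCOVAs:** add injection site as a fixed effect to each change-from-baseline model and to the AUC model.

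The changes should be made before treatment unmasking. They cost wording and, in each ANCOVA, two degrees of freedom. The stratum is already handled in the IWRS, so conduct, dosing, data collection and sample size do not change.

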9.5.4 Secondary clinical efficacy (PD) endpoints

- Time to first plasma glucose concentration of ≥ 70 mg/dL (3.9 mmol/L) without administration of rescue IV glucose.
- Plasma glucose response as area under the curve above baseline from time zero to 30 minutes, $AUC_{0-30min}$.

Secondary clinical efficacy endpoints will be assessed based on plasma concentration data from samples collected at the dosing visit (Visit 2).

Unless otherwise stated, the population base of analysis will be the FAS.

9.5.4.1 Analysis of secondary clinical efficacy (PD) endpoints

1. Time to first plasma glucose concentration ≥ 70 mg/dL from baseline. This time-to-event endpoint will be evaluated using a Kaplan-Meier approach, with treatment group as a stratification factor, analogous to that used for the primary endpoint analysis. Differences between the KM curves (dasiglucagon versus placebo, GlucaGen versus placebo) will be evaluated inferentially using pairwise two-sided log rank tests. If the ≥ 70 mg/dL endpoint is not met within 45 minutes post-dosing, the time of the last valid plasma glucose measurement up to 45 minutes will be the censoring time.
2. The AUC will be calculated as the baseline-adjusted area under the plasma glucose profile over time:
 - a. $AUC_{0-30min}$: restricting the time window to the 0 to 30 minutes interval.
3. The log-transformed AUC endpoint will be analyzed using an analysis of covariance (ANCOVA) model with treatment as fixed effect and baseline plasma glucose modeled as a covariate. The least squares means treatment group differences will be back-transformed (anti-logged) for presentation as a ratio of the treatment group geometric means, with their corresponding 95% CI.

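### Time to 70 mg/dL is compared by an unadjusted log-rank test although the measured baseline glucose sets how far each subject must rise; the test is valid, but a baseline-adjusted model should be added

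*Protocol*

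**What the plan says.** Section 9.5.4 defines the endpoint as an absolute level: "Time to first plasma glucose concentration of ≥ 70 mg/dL (3.9 mmol/L) without administration of rescue IV glucose". Section 9.5.4.1 item 1 gives the method: "This time-to-event endpoint will be evaluated using a Kaplan-Meier approach, with treatment group as a stratification factor". Differences between the curves "will be evaluated inferentially using pairwise two-sided log rank tests", for dasiglucagon and for GlucaGen, each against placebo. For subjects who do not reach the level, "the time of the last valid plasma glucose measurement up to 45 minutes will be the censoring time".

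Section 8.2.3.1 sets the glucose range at dosing: "If plasma glucose is ≥ 45 mg/dL and < 60 mg/dL (2.5-3.3 mmol/L), study treatment (IMP) will be administered". It also fixes when baseline is taken: "The samples are the baseline samples and should be collected within 2 minutes before IMP administration".

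Elsewhere the protocol does use baseline glucose. The additional Cox model for the primary endpoint has "baseline plasma glucose modeled as a continuous covariate" (section 9.5.2.1). The change-from-baseline analyses in section 9.5.3.1 are ANCOVAs with baseline glucose. The glucose AUC over 0 to 30 minutes, in item 3 of section 9.5.4.1 itself, is analyzed with "treatment as fixed effect and baseline plasma glucose modeled as a covariate".

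**The concern.** The distance to the event differs between subjects by a factor of up to 2.5, and a measured value determines it. For the primary endpoint every subject needs the same 20 mg/dL rise. Here a subject starting at 59 needs 11 mg/dL and one starting at 45 needs 25. If the analysis ignores this, known baseline variation is treated as noise, and a chance difference in mean baseline between arms moves the curves apart or together. Section 6.2 stratifies randomization by injection site and not by baseline glucose, so the design does not remove such a difference.

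At stake are the precision of the comparisons with placebo and the side-by-side reading of dasiglucagon and GlucaGen, which serves the secondary objective. Phase 2 responses to those two were comparable (section 2.1.3.1), so a small baseline gap could matter more there than against placebo.

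**Working it through.** **Inputs from the protocol.** Threshold 70 mg/dL (9.5.4); baseline 45 to below 60 mg/dL (8.2.3.1); 78 versus 39 subjects, two-sided 5%, 80% versus 50% recovery within 20 minutes, power 90% (9.1); glucose samples at 4, 6, 8, 10, 12, 15, 17, 20, 25, 30 and 40 minutes before the 45-minute limit (8.2.3.1).

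**Inputs not in the protocol, assumed.** Baseline spread: uniform on 45–60, or normal with mean 54 and SD 3. Rate of glucose rise: lognormal with log-SD 0.3 to 0.5.

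**1. The protocol's own power figure.** Pooled proportion = (78 × 0.8 + 39 × 0.5)/117 = 0.70. Null SE = √(0.7 × 0.3 × (1/78 + 1/39)) = 0.0899. Alternative SE = √(0.16/78 + 0.25/39) = 0.0920. Power = Φ((0.30 − 1.96 × 0.0899)/0.0920) = 91.1%. Other methods give 90.3% (unpooled), 90.7% (arcsine) and 88.9% (exact Fisher). The stated 90% is reproduced. It concerns a 20 mg/dL rise within 20 minutes; the protocol gives no power for the 70 mg/dL endpoint.

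**2. Required rise.** 70 − 60 = 10 (not attained, since baseline is below 60) up to 70 − 45 = 25 mg/dL. With a uniform baseline the mean is 70 − 52.5 = 17.5, the SD is 15/√12 = 4.33 and the CV is 4.33/17.5 = 25%.

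**3. Chance imbalance in mean baseline, 95% range.** 1.96 × SD × √(1/78 + 1/39), where the root is 0.196.
- SD 4.33: ±1.7 mg/dL, about 10% of the 17.5 mean rise (1.7/17.5).
- SD 3: ±1.15, rounded to ±1.2 mg/dL, about 7% of a mean rise of 70 − 54 = 16.

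**4. Power at the design assumption.** Simulation of 78 versus 39 with a 4-minute lag, rise rates calibrated so that 80% and 50% gain 20 mg/dL by 20 minutes, events read on the sampling grid, and 400 replicates per scenario. It compares the log-rank test with a Cox likelihood ratio test that includes baseline.
- 80% versus 50%: about 85–96% unadjusted and 94–98% adjusted, a gain of about 0–11 points. A repeat for this write-up fell inside both ranges. The largest gain came with a uniform baseline and log-SD 0.3, and the smallest with the narrow baseline and log-SD 0.5.
- 70% versus 50%, a smaller effect than the protocol assumes: 44–63% unadjusted and 57–66% adjusted over two runs.
- 90% versus 50%: about 100% for both.

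Monte Carlo standard error near 90% power is √(0.9 × 0.1/400) = 1.5 points.

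**5. Power under a simpler model.** No lag, time to event = (70 − baseline)/rate; log-rank versus adjusted Cox:

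| Ratio of median rates | Baseline | Log-SD | Log-rank | Adjusted |
|---|---|---|---|---|
| 1.15 | uniform | 0.3 | 38.5% | 58.4% |
| 1.15 | uniform | 0.5 | 18.3% | 25.0% |
| 1.25 | uniform | 0.4 | 58.8% | 70.2% |
| 1.25 | SD 3 | 0.4 | 67.3% | 73.3% |
| 1.35 | uniform | 0.3 | 95.8% | 99.8% |
| 1.8 vs 0.4 mg/dL per min | uniform | 0.4 | 100% | 100% |

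**6. Type I error of the log-rank test.** No treatment effect, uniform baseline, log-SD 0.4, 6000 replicates: 4.9% overall. Among trials with a mean-baseline difference of at least 1, 1.5 or 2 mg/dL (23%, 7% and 1.7% of trials) it was 10.9%, 15.7% and 21.6%.

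**The case against.** The strongest reply is that section 9.5.4.1 mirrors the confirmatory method. The primary test in section 9.5.2.1 is itself an unadjusted log-rank test. The Cox model with baseline is additional there, and is run only if hazards look proportional and no more than two-thirds of times are censored in each group. That stands: a reader might infer that the protocol adjusts the primary comparison and forgets to adjust this one, and the text does not support that. The reference to the primary analysis qualifies the Kaplan-Meier approach and does not bring the Cox model with it, so the adjusted model remains absent for this endpoint.

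Second, the endpoint is listed among the other secondary endpoints (section 3.5) and is not in the testing order of section 9.5.1; dasiglucagon versus GlucaGen is descriptive only. This also stands and limits the weight.

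Third, a uniform baseline over 45–60 is a wide assumption. Insulin is titrated towards 55 mg/dL and stopped below 60, which favors clustering in the 50s. The narrower SD of 3 is therefore carried throughout as the lower end.

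Fourth, section 9 lets the SAP refine the analyses. It may do so, but the protocol states a method here rather than leaving it open. The synopsis line that clinical efficacy variables are analyzed like the change-from-baseline variables does not fill the gap, because ANCOVA does not suit a censored time.

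**Conclusion.** The point holds as an inexpensive improvement to a valid analysis. Section 9.5.4.1 item 1 leaves out a measured covariate that arithmetically sets the distance to the event. At the protocol's 80% versus 50% the cost is about 0 to 11 power points. It grows for smaller effects and vanishes for very large ones. Phase 2, where every subject reached 70 mg/dL within 30 minutes at all dose levels, suggests a large contrast with placebo. The benefit would then be mainly precision, robustness to imbalance and an effect estimate with an interval.

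Three stronger readings are not supported:
- **The test is invalid.** Overall type I error is about 5%. The higher rates apply only conditionally on an imbalance, and the larger imbalances are uncommon.
- **The comparison is badly underpowered.** Power near 50% needs a 70% versus 50% contrast, which the protocol does not assume.
- **The planned analysis is biased.** In simulation at 70% versus 50% the log rate ratio was 8–33% larger after adjustment. Part of that is non-collapsibility: a conditional and a marginal rate ratio are different quantities.

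All sizes depend on assumed baseline spread and response variability, which the protocol does not give.

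**What to change.** In section 9.5.4.1 item 1, keep the Kaplan-Meier curves and the pairwise log-rank tests. Add a Cox model with treatment group and continuous baseline plasma glucose, reporting the rate ratio and 95% CI, subject to the same proportional-hazards and censoring conditions as section 9.5.2.1.

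Alternatively, stratify the log-rank test by baseline category (45 to <50, 50 to <55, 55 to <60 mg/dL), with a pre-specified rule for merging sparse categories.

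The cost is one sentence and one extra model; the data are already collected. The stratified version has the drawback of small placebo strata: 39/3 = 13 subjects each if evenly spread, and possibly far fewer in the lowest category. The Cox model is the better choice for that reason.
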